## MODIFICATION HISTORY

Unique Identifier for this Version	Date of the Document Version	Author	Significant Changes from Previous Version
1.0	21Jan2022	PPD	Not Applicable – First Version
2.0	26May2023	PPD	
Additional secondary objective and corresponding estimand added along with additional categories in appendix 7 to bring in line with Protocol v4.0.
 
Addendum added to limit the scope of the final analysis due to the study terminating early due to lack of enrollment.
 
Modifications to Visit windowing, IAS analysis set inclusion criteria and GMT calculations update to clarify planned analyses

## 1. INTRODUCTION

This statistical analysis plan (SAP) describes the rules and conventions to be used in the presentation and analysis of immunogenicity and safety data for protocol D8111C00010. It describes the data to be summarized and analyzed, including specifics of the statistical analyses to be performed.

This SAP is based on protocol amendment 4.0, dated 31Mar2022.

## 2. STUDY OBJECTIVES AND ESTIMANDS

### 2.1. PRIMARY OBJECTIVE

The primary immunogenicity objective is to characterize the immunogenicity of a 2-dose primary vaccination with AZD1222 with a 4-week dosing interval in SARS-CoV-2 naïve immunocompromised adults and immunocompetent adults  $\geq 18$  years.

### 2.2. SECONDARY OBJECTIVES

The secondary safety objective is to characterize the reactogenicity and safety of a 3-dose primary vaccination series with AZD1222 with a 4-week dosing interval in SARS-CoV-2 naïve immunocompromised adults  $\geq 18$  years.

The immunogenicity secondary objectives are:

- To characterize the immunogenicity after a 3rd-dose in a 3 dose primary vaccination series with AZD1222 in immunocompromised adults  $\geq 18$  years.
- To describe the immunogenicity of a 2-dose primary vaccination with AZD1222 in adults  $\geq 18$  years with 4-week dosing interval between SARS-CoV-2 naïve participants with the below conditions compared to immunocompetent participants:
  - Solid organ transplant
  - Hematopoietic stem cell transplant
  - Solid organ cancer patients receiving cytotoxic chemotherapy

- Chronic inflammatory disorders
- Primary immunodeficiency
- Any immunocompromised condition, pooled populations above
- To describe the immunogenicity after the 3rd dose in a 3-dose primary vaccination series with AZD1222 in adults  $\geq 18$  years between SARS-CoV-2 naïve immunocompromised participants (see above conditions) compared to immunocompetent participants after a 2-dose primary vaccination.
- To describe the immunogenicity of the AZD1222 vaccination between 28 days post 3rd-dose compared to 28 days post 2nd-dose, in adults  $\geq 18$  years between SARS-CoV-2 naïve immunocompromised and immunocompetent participants.
- To characterize the immunogenicity after a 3rd-dose booster vaccination of AZD1222, administered 6 months after dose 1 of a 2-dose primary vaccination with AZD1222, in immunocompetent adults  $\geq 18$  years.

## 2.3. EXPLORATORY OBJECTIVES

The exploratory objectives are:

- To monitor the occurrence of COVID-19 in immunocompromised adults  $\geq 18$  years that have received 2 doses of AZD1222.
- To further describe humoral and cell mediated responses to AZD1222 following administration of AZD1222 in immunocompromised adults  $\geq 18$  years of age.
- To explore correlations between anti-S, pseudo-neutralization, and ChAdOx1 nAb antibody titres.

## 2.4. ESTIMANDS

The primary and secondary estimands to support regulatory decisions are described in the following table:

**Table A: List of Estimands**

Estimand	Attributes				
	Population	Treatment Condition of Interest	Variable/Endpoint	Intercurrent event handling strategy	Population-level summary measure
The immunogenicity of a 2-dose primary vaccination with AZD1222 with a 4-week dosing interval in SARS-CoV-2 naïve immunocompromised adults and immunocompetent adults $\geq 18$ years.	SARS-CoV-2 naïve immunocompromised adults and immunocompetent adults $\geq 18$ years, who don't have exclusionary important protocol deviations (IPDs) and received at least one IM dose of AZD1222.	2 IM doses of AZD1222 with a 4-week dosing interval	a) SARS-CoV-2 specific GMTs in SARS-CoV-2 S and Neutralizing antibodies  b) A binary response, whereby participants who have a post-treatment seroresponse ( $\geq 4$ -fold rise in titres from day of baseline value to 28 days post each dose) as measured by the S and Neutralizing antibodies	For participants who withdraw from the study, or who use restricted medications judged to have the potential to interfere with the generation or interpretation of an immune response, absence of data following these participants' withdrawal or subsequent data following the IPDs will be treated as missing.  Participants who (1) did not receive their second dose of AZD1222 or (2) tested positive	a) GMTs 28 days post each dose in SARS-CoV-2 S and Neutralizing antibodies  b) Number and percentage of participants achieving a seroresponse ( $\geq 4$ -fold rise in titres from day of baseline value to 28 days post each dose) as measured by the S and Neutralizing antibodies

				for SARS-CoV-2 infection (RT-PCR) will be censored at day 29/ the date of the positive test, whichever is earliest.	
The immunogenicity of a 2-dose primary vaccination with AZD1222 in adults $\geq 18$ years with a 4-week dosing interval between SARS-CoV-2 naïve immunocompromised participants compared to immunocompetent participants.	SARS-CoV-2 naïve immunocompromised adults and immunocompetent adults $\geq 18$ years, who don't have exclusionary important protocol deviations (IPDs) and received 2 IM doses of AZD1222.	2 IM doses of AZD1222 with a 4-week dosing interval	a) SARS-CoV-2 specific GMTs in SARS-CoV-2 S and Neutralizing antibodies  b) A binary response, whereby participants who have a post-treatment seroresponse ( $\geq 4$ -fold rise in titres from day of baseline value to 28 days post second dose) as measured by the S and Neutralizing antibodies	For participants who withdraw from the study, did not receive 2 IM doses of AZD1222, or who use restricted medications judged to have the potential to interfere with the generation or interpretation of an immune response, absence of data following these participants' withdrawal or subsequent data following the IPDs will be treated as missing.  Participants who tested positive for SARS-CoV-2 infection (RT-PCR) will be censored at the date of the positive test.	a) Ratio of post-treatment GMTs from day of baseline value to 28 days post second dose in SARS-CoV-2 S and Neutralizing antibodies between each SARS-CoV-2 naïve immunocompromised cohort (including the pooled immunocompromised cohort) and the immunocompetent participants  b) Difference in percentages of participants who have a post-treatment seroresponse ( $\geq 4$ -fold rise in titres from day of baseline value to 28 days post second dose) as measured by the S and

CC1

					Neutralizing antibodies between each SARS-CoV-2 naïve immunocompromised cohort (including the pooled immunocompromised cohort) and the immunocompetent participants
The immunogenicity of a 3-dose primary vaccination with AZD1222 with a 4-week dosing interval in SARS-CoV-2 naïve immunocompromised adults $\geq 18$ years.	SARS-CoV-2 naïve immunocompromised adults $\geq 18$ years, who don't have exclusionary important protocol deviations (IPDs) and received at 3 IM doses of AZD1222.	3 IM doses of AZD1222 with a 4-week dosing interval	a) SARS-CoV-2 specific GMTs in SARS-CoV-2 S and Neutralizing antibodies  b) A binary response, whereby participants who have a post-treatment seroresponse ( $\geq 4$ -fold rise in titres from day of baseline value to 28 days post third dose) as measured by the S and Neutralizing antibodies	For participants who withdraw from the study, did not receive 3 IM doses of AZD1222, or who use restricted medications judged to have the potential to interfere with the generation or interpretation of an immune response, absence of data following these participants' withdrawal or subsequent data following the IPDs will be treated as missing.  Participants who tested positive for SARS-CoV-2 infection	a) GMTs 28 days post third dose in SARS-CoV-2 S and Neutralizing antibodies  b) Number and percentage of participants achieving a seroresponse ( $\geq 4$ -fold rise in titres from day of baseline value to 28 days post third dose) as measured by the S and Neutralizing antibodies

				(RT-PCR) will be censored at the date of the positive test.	
Sensitivity analysis- The immunogenicity of a 3-dose primary vaccination with AZD1222 with a 4-week dosing interval in SARS-CoV-2 naïve immunocompromised adults $\geq 18$ years.	SARS-CoV-2 naïve immunocompromised adults $\geq 18$ years, who don't have exclusionary important protocol deviations (IPDs) and received at 3 IM doses of AZD1222.	3 IM doses of AZD1222 with a 4-week dosing interval	A binary response, whereby participants who have a post-treatment seroresponse ( $\geq 4$ -fold rise in titres from visit 8 [pre-dose 3] to 28 days post third dose) as measured by the S and Neutralizing antibodies	For participants who withdraw from the study, did not receive 3 IM doses of AZD1222, or who use restricted medications judged to have the potential to interfere with the generation or interpretation of an immune response, absence of data following these participants' withdrawal or subsequent data following the IPDs will be treated as missing.  Participants who tested positive for SARS-CoV-2 infection (RT-PCR) will be censored at the date of the positive test.	Number and percentage of participants achieving a seroresponse ( $\geq 4$ -fold rise in titres from visit 8 value [pre-dose 3] to 28 days post third dose) as measured by the S and Neutralizing antibodies
The immunogenicity of	SARS-CoV-2 naïve immunocompromised	3 IM doses of AZD1222	a) SARS-CoV-2 specific GMTs in SARS-CoV-2 S and Neutralizing	For participants who withdraw from the study, did not receive	a) Ratio of post-treatment GMTs from day of baseline value to 28


a 3-dose primary vaccination with AZD1222 in adults <math>\geq 18</math> years with a 4-week dosing interval for SARS-CoV-2 naïve immunocompromised participants compared to immunocompetent participants after 2-dose primary vaccination.
	
participants <math>\geq 18</math> years, who don't have exclusionary important protocol deviations (IPDs) and received 3 IM doses of AZD1222 (2 IM doses of AZD1222 for immunocompetent participants).
	
with a 4-week dosing interval (2 IM doses of AZD1222 for immunocompetent participants)
	
antibodies  b) A binary response, whereby participants who have a post-treatment seroresponse (<math>\geq 4</math>-fold rise in titres from day of baseline value to 28 days post third dose [28 days post second dose for immunocompetent participants]) as measured by the S and Neutralizing antibodies
	
3 IM doses of AZD1222 (2 IM doses of AZD1222 for immunocompetent participants), or who use restricted medications judged to have the potential to interfere with the generation or interpretation of an immune response, absence of data following these participants' withdrawal or subsequent data following the IPDs will be treated as missing.  Participants who tested positive for SARS-CoV-2 infection (RT-PCR) will be censored at the date of the positive test.
	
days post third dose (28 days post second dose for immunocompetent participants) in SARS-CoV-2 S and Neutralizing antibodies between each SARS-CoV-2 naïve immunocompromised cohort (including the pooled immunocompromised cohort) and the immunocompetent participants  b) Difference in percentages of participants who have a post-treatment seroresponse (<math>\geq 4</math>-fold rise in titres from day of baseline value to 28 days post third dose [28 days post second dose for immunocompetent participants]) as measured by the S and Neutralizing antibodies between each SARS-CoV-2 naïve

----------------------------------------------------------------------------------------------------------------------------------------------------------------------------------------------------------------------------------------------------	---------------------------------------------------------------------------------------------------------------------------------------------------------------------------------------------------------------	-----------------------------------------------------------------------------------------------	---------------------------------------------------------------------------------------------------------------------------------------------------------------------------------------------------------------------------------------------------------------------------------------------------------------------------	-------------------------------------------------------------------------------------------------------------------------------------------------------------------------------------------------------------------------------------------------------------------------------------------------------------------------------------------------------------------------------------------------------------------------------------------------------------------------------------------	-------------------------------------------------------------------------------------------------------------------------------------------------------------------------------------------------------------------------------------------------------------------------------------------------------------------------------------------------------------------------------------------------------------------------------------------------------------------------------------------------------------------------------------------------------------------------------------------------------------------------

[figure not shown]
					immunocompromised cohort (including the pooled immunocompromised cohort) and the immunocompetent participants
To describe the immunogenicity of the AZD1222 vaccination between 28 days post 3rd-dose compared to 28 days post 2nd-dose, in adults $\geq$ 18 years between SARS-CoV-2 naïve immunocompromised and immunocompetent participants.	SARS-CoV-2 naïve immunocompromised adults and immunocompetent adults $\geq$ 18 years, who don't have exclusionary important protocol deviations (IPDs) and received at least one IM dose of AZD1222.	3 IM doses of AZD1222 with a 4-week dosing interval	a) Ratio of SARS-CoV-2 specific GMT titres  b) Difference in seroresponse rates of SARS-CoV-2 specific titres ( $\geq$ 4-fold increase in titres from 28 days post dose 2 to 28 days post dose 3)	For participants who withdraw from the study, did not receive 3 IM doses of AZD1222, or who use restricted medications judged to have the potential to interfere with the generation or interpretation of an immune response, absence of data following these participants' withdrawal or subsequent data following the IPDs will be treated as missing.  Participants who tested positive for SARS-CoV-2 infection (RT-PCR) will be censored at	a) Ratio of post-treatment GMTs from 28 days post second dose to 28 days post third dose in SARS-CoV-2 S and Neutralizing antibodies for each SARS-CoV-2 naïve immunocompromised cohort (including the pooled immunocompromised cohort) and the immunocompetent participants  b) Difference in percentages of participants who have a post-treatment seroresponse ( $\geq$ 4-fold rise in titres from 28 days post second dose to 28 days post third dose) as measured by the S and

				the date of the positive test.	Neutralizing antibodies for each SARS-CoV-2 naïve immunocompromised cohort (including the pooled immunocompromised cohort) and the immunocompetent participants
The immunogenicity of a 3-dose booster vaccination with AZD1222, administered 6 months after dose 1 of a 2-dose primary vaccination in SARS-CoV-2 naïve immunocompetent adults $\geq 18$ years.	SARS-CoV-2 naïve immunocompetent adults, who don't have exclusionary important protocol deviations (IPDs) and received 3 IM doses of AZD1222.	3 IM doses of AZD1222 with a 4-week dosing interval between doses 1 and 2 and a 6 month interval after dose 1.	a) SARS-CoV-2 specific GMTs in SARS-CoV-2 S and Neutralizing antibodies  b) A binary response, whereby participants who have a post-treatment seroresponse ( $\geq 4$ -fold rise in titres from day of baseline value to 28 days post third dose) as measured by the S and Neutralizing antibodies	For participants who withdraw from the study, or who use restricted medications judged to have the potential to interfere with the generation or interpretation of an immune response, absence of data following these participants' withdrawal or subsequent data following the IPDs will be treated as missing.  Participants tested positive for SARS-CoV-2 infection (RT-PCR) will be censored at the	a) GMTs 28 days post third dose in SARS-CoV-2 S and Neutralizing antibodies  b) Number and percentage of participants achieving a seroresponse ( $\geq 4$ -fold rise in titres from day of baseline value to 28 days post third dose) as measured by the S and Neutralizing antibodies

CCI

				date of the positive test.	
--	--	--	--	----------------------------	--

CCI

A large black rectangular redaction box covers the majority of the page content below the table. In the top left corner of this redacted area, the letters "CCI" are printed in red.

[figure not shown]

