## 6.4. WINDOWING CONVENTIONS

A windowing convention will be used to determine the analysis value for a given study visit for immunogenicity . The window definitions as following will be used:

1. A window of +/- 7 days from the target day is applied to the V1+14, V1+28, V5+14, V5+28 and V8+28 visits for the immunocompromised participants and to the V1+14, V1+28, V5+14, V5+28 and V9+28 visits for the immunocompetent participants.
2. A window of +/- 30 days from the target day is applied to the V1+182 and V1+364 visits for the immunocompromised participants and to the V1+182 and V1+364 visits for the immunocompetent participants.

One or more results for a particular variable may be obtained in the same visit window. In such an event, the result with the date closest to the expected visit date will be used in the analysis. In the event that two observations are equidistant from the expected visit date, the later observation will be used in the analysis.

**Table D:** Analysis windows for Immunogenicity by Visit (Immunocompromised participants)

Dosing Period	Visit	Day Relative to Dose within the Dosing Period (a)	Visit Window (Study Day) Relative to the Dosing Period
Relative to Dose 1	Baseline (V1)	≤ 1	≤ 1
	V3	15	8 – 21
	V5	29	22 – 35
Relative to Dose 2	V7	15	8 – 21
	V8	29	22 – 35
Relative to Dose 3	V10	29	22 – 35
Relative to Dose 1	V11	183	153 - 212
	V12	365	335 - 394

(a) For each dosing period, the administration of the study intervention is designated as Study Day 1. For analyses within a period, the study day value is incremented by 1 for each date following the vaccine administration. Dates prior to the vaccine administration are decremented by 1, with the date preceding the vaccine administration designated as Study Day -1 (there is no Study Day 0).

**Table E:** Analysis windows for Immunogenicity by Visit (Immunocompetent Participants)

Dosing Period	Visit	Day Relative to Dose within the Dosing Period (a)	Visit Window (Study Day) Relative to the Dosing Period
Relative to Dose 1	Baseline (V1)	≤ 1	≤ 1
	V3	15	8 – 21
	V5	29	22 – 35
Relative to Dose 2	V7	15	8 – 21
	V8	29	22 – 35
Relative to Dose 1	V9	183	153 - 212
Relative to Dose 3	V10	29	22 – 35
Relative to Dose 1	V11	365	335 - 394

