## 16. IMMUNOGENICITY ENDPOINTS

Unless otherwise indicated, all immunogenicity summaries and figures will be presented by cohort (including the pooled immunocompromised cohort) and visit, when appropriate, based on the immunogenicity analysis set.

For all immunogenicity endpoints, participants will be censored at the date of first positive PCR test for SARS-CoV-2 infection/non-study COVID-19 vaccine administration/exclusionary restricted medication, whichever occurs first, such that data from all visits after the date of first positive PCR test for SARS-CoV-2 infection/non-study COVID-19 vaccine administration/exclusionary restricted medication will be excluded from derivations and all by-visit summaries. All immunogenicity data regardless of censoring will be listed for all participants, with all censored assessments flagged.

For summaries over time, participants who do not receive dose 2 of study intervention will be excluded from all time points post dose 2. Participants who do not receive dose 3 of study intervention will be excluded from all time points post dose 3.

All participants will be assessed for serum samples for SARS-CoV-2 serology testing.

The immunogenicity primary endpoints are:

- Post-treatment GMTs and GMFRs from day of dosing baseline value to 28 days post dose 1 and dose 2 in SARS-CoV-2 S antibodies.
- Proportion of participants who have a post-treatment seroresponse ( $\geq 4$ -fold rise in titres from day of dosing baseline value to 28 days post dose 1 and dose 2) for the S antibodies.
- Post-treatment GMTs and GMFRs from day of dosing baseline value to 28 days post dose 1 and dose 2 in SARS-CoV-2 neutralizing antibodies (pseudo-neutralization assay)
- Proportion of participants who have a post-treatment seroresponse ( $\geq 4$ -fold rise in titres from day of dosing baseline value to 28 days post dose 1 and dose 2) as measured by SARS-CoV-2 neutralizing antibodies (pseudo-neutralization assay)

The immunogenicity secondary endpoints are:

- Ratio of post-treatment GMTs at 28 days post second dose in SARS-CoV-2 S antibodies between each immunocompromised cohort (including the pooled immunocompromised cohort) and immunocompetent participants.

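### The Day 29 cut-off in the primary estimand conflicts with the V5 window and Section 16, and is ambiguous for participants who test RT-PCR positive later

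*SAP*

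**What the plan says.** **Primary row of Table A (SAP Section 2.4).** The population is people who "received at least one IM dose of AZD1222", and the first summary measure is "GMTs 28 days post each dose in SARS-CoV-2 S and Neutralizing antibodies", with seroresponse at the same times. A participant who stops after dose 1 therefore still counts towards the post-dose-1 result. One sentence handles two intercurrent events. It opens "Participants who (1) did not receive their second dose of AZD1222 or (2) tested positive" for infection by RT-PCR, and says that these participants "will be censored at day 29/ the date of the positive test, whichever is earliest".

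**Section 16.** For every immunogenicity endpoint, "participants will be censored at the date of first positive PCR test for SARS-CoV-2 infection/non-study COVID-19 vaccine administration/exclusionary restricted medication, whichever occurs first". On a missed second dose, "participants who do not receive dose 2 of study intervention will be excluded from all time points post dose 2". Day 29 does not appear.

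**Section 6.4.** "A window of +/- 7 days from the target day is applied to the V1+14, V1+28, V5+14, V5+28 and V8+28 visits" for the immunocompromised cohorts, and the V5 rule for immunocompetent participants is the same. Tables D and E give V5 a target of Day 29 and a window of Days 22–35, both counted from dose 1.

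**Second row of Table A (two doses, compared with immunocompetent participants).** "Participants who tested positive for SARS-CoV-2 infection (RT-PCR) will be censored at the date of the positive test". The later rows use the same rule.

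**Addendum.** It reduces the set of outputs but leaves the censoring rules alone, and refers to the main SAP for everything that it does not change.

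**The concern.** The estimand table and the analysis section give different instructions for samples that feed the primary endpoint.

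The first conflict concerns participants without dose 2. Their V5 sample is a valid post-dose-1 value anywhere in its window, yet the primary row cuts them off on the window's target day. Whether the sample counts would depend on whether the visit ran a few days late.

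The second problem concerns participants who received both doses and tested positive later. If the sentence means the minimum of Day 29 and the test date, an infection months after V8 removes a V8 value obtained before it. Post-dose-2 data would then be selected on a later event. The same sample would be missing under the primary row, but present under Section 16 and under the Table A rows that use a post-dose-2 value. A programmer could defend either dataset.

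**Working it through.** The SAP states no figure on this point, so there is none to reproduce. The check lists which samples survive under each rule.

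**Inputs**
- V5 window: Days 22–35 from dose 1 (Tables D and E).
- V7 and V8 windows: Days 8–21 and 22–35 from dose 2 (same tables).
- Assumption: dose 2 falls on its nominal Day 29. Day k from dose 2 is then Study Day 29 + k − 1.

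**V5 for a participant without dose 2**
- Window length: 35 − 22 + 1 = 14 days.
- Days after Day 29: 30 to 35, which is 6 days, and 6/14 = 43%. If Day 29 itself is also cut, 7 of 14.
- The text of Section 6.4 (7 days either side of Day 29) would run to Day 36, one day beyond the tables. I use the tabulated limits.
- Section 16 keeps all 14 days, because V5 is tabulated relative to dose 1 and is not a time point after dose 2.

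**V7 and V8 for a participant with two doses**
- V7: Study Days 29 + 8 − 1 = 36 to 29 + 21 − 1 = 49, target 29 + 15 − 1 = 43.
- V8: Study Days 29 + 22 − 1 = 50 to 29 + 35 − 1 = 63, target 29 + 29 − 1 = 57.

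**Censoring day under three rules.** Literal means the minimum of Day 29 and the test date for anyone in either group. Paired means Day 29 for a missed dose 2, the test date for infection, and the earlier if both apply.

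| Dose 2 | RT-PCR positive | Table A, literal | Table A, paired | Section 16 |
|---|---|---|---|---|
| Yes | Never | None | None | None |
| Yes | Day 20 | 20 | 20 | 20 |
| Yes | Day 50 | 29 | 50 | 50 |
| Yes | Day 100 | 29 | 100 | 100 |
| No | Never | 29 | 29 | None; post-dose-2 time points dropped |
| No | Day 20 | 20 | 20 | 20; post-dose-2 time points dropped |
| No | Day 100 | 29 | 29 | 100; post-dose-2 time points dropped |

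**Reading the table**
- Without dose 2 and not positive before Day 30, both readings of Table A give Day 29 and Section 16 does not. The Day 30–35 conflict does not depend on how the sentence is parsed.
- With two doses and a positive test on Day 100, the literal reading removes all of V7 (Days 36–49) and V8 (Days 50–63). It would also remove a V5 sample taken on Days 30–35. The paired reading and Section 16 keep them.
- With two doses and no positive test, no rule censors anything.

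**The case against.** The strongest reply is that the sentence numbers two groups and then gives two times separated by a slash. Pairing them in order is natural, with the closing phrase covering people in both groups. That reading agrees with Section 16 and with the other Table A rows, and it spares the row's own post-dose-2 endpoint. This stands: the V7/V8 loss is a consequence of one reading and is not certain. It does not settle the matter, because the sentence lacks the word that would make the pairing explicit. Section 16 uses the same form, a slash-separated list closed by a whichever phrase, and there it plainly means the minimum.

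The second reply is that Day 29 may simply name the V5 visit, whose target day it is. That would remove the Day 30–35 conflict. It is possible, but the row sets Day 29 against a calendar date and asks for the earlier, which treats it as a date.

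Three stronger inferences are tempting and unsupported:
- **That every other Table A row keeps the disputed post-dose-1 samples.** Those rows have no endpoint after dose 1 alone, and the second row treats participants without two doses as missing. For V5 the conflict is with Section 16 and Tables D and E only.
- **That the primary GMT is biased upward by a known amount.** If a share p later test positive with V8 titres k-fold lower, dropping them multiplies the GMT by k^p: 2^0.1 = 1.07 up to 4^0.3 = 1.52. Both p and k are assumed, the SAP gives neither, and the formula applies only under the literal reading.
- **That primary and secondary results will rest on different people.** The addendum drops between-arm comparisons, which removes the second row's contrast. The disagreement with Section 16 remains.

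**Conclusion.** The point holds as a conflict in one part and an ambiguity in the other.

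For participants without dose 2, a Day 29 cut-off removes in-window V5 samples from Days 30–35 (6 of 14 window days) that Section 16 retains. This is true under both the literal and the paired reading; only taking Day 29 as a label for the V5 visit avoids it. The 43% is a share of calendar days, not of samples or participants.

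For RT-PCR-positive participants, the sentence permits a reading that deletes valid pre-infection V7 and V8 values and another that keeps them.

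Only participants without dose 2 or with a positive RT-PCR are touched. The effect on the GMTs and seroresponse rates cannot be derived, because the SAP gives no rate of missed second doses or infections.

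Two assumptions remain: dose 2 on Day 29 for the V7 and V8 study days, and that the primary summaries are still produced. The addendum drops by-visit summary tables without saying whether these are among them. It also reports a sample much smaller than planned, so each value removed carries more weight.

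**What to change.** Replace the censoring sentence in the primary row of Table A with a separate rule for each event, aligned to Section 16, for example:

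> A participant who does not receive dose 2 contributes samples up to and including the V5 analysis window (Days 22–35) and none from time points after dose 2. Every participant is censored at the earliest of the first positive RT-PCR test, a non-study COVID-19 vaccine, and an exclusionary restricted medication.

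Delete the Day 29 cut-off and the phrase that takes the earlier of it and the test date. Naming the non-study vaccine matters: Section 16 censors for it and the primary row does not mention it, so correcting only the infection and dose 2 rules would leave the two sections different.

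The cost is a short text change in Table A and a check that the censoring flag is programmed to it. No new data are needed.
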